9.4.1.2. Secondary Analyses

OS Rate at 12, 24 and 36 months

The non-parametric Kaplan-Meier method will be used to estimate the survival curves. OS rate at 12 months, 24 months and 36 months and the corresponding 95% CI will be estimated from the Kaplan-Meier analysis.

Overall Response Rate/Disease Control Rate

ORR per RECIST v1.1 is defined as the proportion of the participants who have a complete response (CR) or partial response (PR) as the best overall response per RECIST v1.1 based upon investigator assessment.

DCR per RECIST v1.1 is defined as the percentage of participants with a best overall response of CR or PR at any time plus SD meeting the minimum time of 18 weeks per RECIST v1.1 based upon investigator assessment.

Stratified Miettinen and Nurminen's method will be used for comparison of the ORR/DCR between two treatment groups. The difference in ORR/DCR and its 95% confidence interval from the stratified Miettinen and Nurminen's method with strata weighting by sample size with a single treatment covariate will be reported. Participants with unknown or missing response will be treated as non-responders and these participants will be included in the denominator when calculating the percentage of ORR and DCR.

Duration of Response

Duration of response (DoR) per RECIST v1.1 is defined as the time from first documented evidence of CR or PR until first documented disease progression per RECIST v1.1 based upon investigator assessment or death due to any cause, whichever occurs first, among participants who demonstrated CR or PR as the best overall response per RECIST v1.1. If sample size permits, DoR per RECIST v1.1 will be summarized descriptively using Kaplan-Meier medians and quartiles.

9.4.1.3. Exploratory Analyses

9.4.1.3.1. Progression-Free Survival per iRECIST (iPFS)

Progression-free survival per iRECIST (iPFS) is defined as the interval of time from the date of randomization to the date of the first documented disease progression confirmed consecutively per iRECIST based on investigator assessment, or death due to any cause, whichever occurs first.

Unlike RECIST 1.1, iRECIST requires the confirmation of progression and uses the terms unconfirmed progressive disease (iUPD) and confirmed progressive disease (iCPD).

The progression event date (iPD date) to be used in the calculation of PFS per iRECIST should be the first date of documented iUPD provided that iCPD is confirmed at the next assessment. If iUPD occurs, but is disregarded because of later iSD, iPR, or iCR, that iUPD date should not be used as the progression event date.

If progression is not confirmed and there is no subsequent iSD, iPR, or iCR, then the iUPD date will be used as iPD date in the following scenarios:

- Participant discontinues study treatment because the participant was judged not to be clinically stable
- Participant does not undergo further response assessments due to any reason (i.e., participant refusal, protocol non-compliance, or participant death)
- Next timepoint response of iUPD, and iCPD never occurs

Determination of dates of iPFS events and dates for censoring in the secondary analysis of iPFS are summarized in [Table 11](#).

Table 11 Censoring Rules for Analysis of iPFS

Situation	Primary Analysis
No baseline disease assessments and the participant has not died	Censored at the date of randomization
No post-baseline disease assessments and the participant has not died	Censored at the date of randomization
With post-baseline disease assessments, new anticancer treatment is not initiated, and no iPD date or death	Censored at the date of last radiological disease assessment
With post-baseline disease assessments, new anticancer treatment is initiated (prior to iPD date or death) ¹	Censored at the date of last radiological disease assessment on or prior to the initiation of new anticancer treatment
iPD date or death after ≤ 1 missed disease assessment	Progressed at the iPD date ² or death
iPD date or death documented after ≥ 2 missed disease assessments	Censored at the date of last radiological disease assessment prior to the ≥ 2 missed disease assessment

Abbreviations: iPD=immune-based progressive disease; iPFS=progression-free survival per iRECIST

1. If the iPD date and new anti-cancer therapy occur on the same day, it is assumed that the progression was documented first (i.e. outcome is progression; the date is the date of the assessment for progression).
2. The earliest date of radiological assessments of lesion in which progression criteria are met for the iPD date.

The non-parametric Kaplan-Meier method will be used to estimate the iPFS curves. The treatment difference in iPFS will be assessed by the stratified log-rank test. A stratified Cox proportional hazard model with Efron's method of tie handling will be used to assess the magnitude of the treatment difference (i.e., hazard ratio) between the treatment arms. The hazard ratio and its 95% confidence interval from the stratified Cox model with Efron's method of tie handling and with a single treatment covariate will be reported.

In case the proportional hazards assumption is not valid for iPFS, the RMST method or piecewise HR as appropriate may be conducted for iPFS to account for the possible non-proportional hazards effect.

9.4.1.3.2. Other Exploratory Analyses

An exploratory analysis of ORR per iRECIST will be performed using the stratified Miettinen and Nurminen's method. The corresponding 95% CI for ORR will also be provided. Participants with unknown or missing responses will be treated as non-responders, i.e., these participants will be included in the denominator when calculating percentages of response.

If sample size permits, DoR per iRECIST will be summarized descriptively using Kaplan-Meier medians and quartiles.

An exploratory analysis of PFS2, defined as the time from randomization to subsequent disease progression per RECIST 1.1 based on investigator assessment after initiation of first new anti-cancer therapy, or death from any cause, whichever first, will be carried out. Participants alive and for whom a second objective disease progression has not been observed will be censored at the last time known to be alive and without second objective disease progression.

Further details of efficacy analyses will be described in the statistical analysis plan.

PK, immunogenicity and biomarker exploratory analyses will be described in the statistical analysis plan. These exploratory analyses may be presented separately from the main CSR.

9.4.2. Safety Analyses

The safety population will serve as the primary population for the analyses of safety data in this study. Safety analyses will follow a tiered approach [Crowe, 2009] as shown in [Table 12](#). The tiers differ with respect to the analyses that will be performed. Tier 1 safety endpoints that will be critical to inferential testing for statistical significance with p-values and 95% confidence intervals may be provided for between-group comparisons.

For this protocol, there are no Tier 1 events. All safety parameters will be considered Tier 2 or Tier 3. Tier 2 parameters will be assessed via point estimates with 95% CI provided for between-group comparisons; only point estimates by treatment group are provided for Tier 3 safety parameters. The between-treatment difference will be analyzed using the Miettinen and Nurminen method.

Based on emerging external data, the analysis strategy for safety endpoints may be modified to improve the integrity and efficiency of the design. Should this happen, the change will be documented elsewhere, if not in a protocol amendment, at the earliest time before any unblinding of the data. Refer to the statistical analysis plan for further details.

Table 12 Analysis Strategy for Safety Parameters

Safety Tier	Safety Endpoint	95% CI for Treatment Comparison	Descriptive Statistics
Tier 2	Any AE	X	X
	Any Serious AE	X	X
	Any Grade 3-5 AE	X	X
	Any Treatment-Related AE	X	X
	Any Treatment-Related Serious AE	X	X
	Any Grade 3-5 and Treatment-Related AE	X	X
	Dose Modification due to AE	X	X
	Discontinuation due to AE	X	X
	Death	X	X
Tier 3	Specific AEs, SOCs (incidence \geq 5% of participants in 1 of the treatment groups)	X	X
	Specific AEs, SOCs (incidence $<$ 5% of participants in both treatment groups)		X
	Change from Baseline Results (Labs, ECGs, Vital Signs)		X

Abbreviations: AE=adverse event; CI=confidence intervals; ECG=electrocardiogram; SOC=system organ class

9.4.3. Patient Reported Outcomes

EORTC IL50 and IL51(subset of domains from the EORTC QLQ C30 and H&N35 respectively) are not pure efficacy or safety endpoints because they are affected by both disease symptoms and treatment tolerability in addition to HRQoL domains.

The time to deterioration (TTD) in Pain measured by the EORTC QLQ-H&N35 pain domain (included in the EORTC IL51) and the TTD in Physical Function (PF) measured by the PROMIS PF 8c will be analysed in the ITT population using the non-parametric Kaplan-Meier method.

The treatment effect in TTD will be assessed separately by the stratified log-rank test. A stratified Cox proportional hazard model with Efron's method of tie handling will be used to assess the magnitude of the treatment difference (i.e., hazard ratio) between the treatment arms. The hazard ratio and its 95% confidence interval from the stratified Cox model with Efron's method of tie handling and with a single treatment covariate will be reported.

For both Pain and PF, TTD will be defined as the time from the date of randomization to the date of first definitive meaningful deterioration in score compared to baseline. The deterioration has to be:

- Meaningful, i.e. greater than a clinically meaningful within-individual change in score, as defined below;
- Definitive, i.e. two sequential assessments of the score are showing a clinically meaningful deterioration compared to baseline and no subsequent scores return to baseline, or no further score is available for the patients for any reason (including disease progression or death)

Patients who don't show meaningful deterioration will be censored at the time of the last available PRO assessment.

As no threshold for meaningful within-individual change is established for the EORTC QLQ-H&N35 pain domain score or PROMIS PF 8c score, the value for use in the TTD analyses will be determined using blinded interim data from the phase II. These analyses will be performed before study unblinding and the value will be set-up before database lock. The full procedure for determination of meaningful within-person change in EORTC QLQ-H&N35 pain domain score and PROMIS PF 8c score will be fully described in the clinical statistical analysis plan or in a standalone analysis plan, as appropriate. It will include anchor-based approach using the patient global impression of severity and change as an anchors, and possibly other clinical anchors (e.g. ECOG status). Supportive distribution-based methods may be applied as sensitivity analyses.

The EORTC IL50, EORTC IL51, BPI-SF I3 and EQ-5D changes will be summarized as part of the exploratory analysis. Longitudinal and descriptive data analysis may be used to evaluate patient reported outcomes. The detailed PRO analysis plan will be included in a reporting and analysis plan document.

9.5. Interim Analyses

If the study continues as a Phase III study, there will be two interim analyses on OS, allowing for early stopping of the study due to efficacy or allow for non-binding futility analysis.

For the Phase III study with no enrollment pause, the timing of the two interim analyses will be triggered by the pre-specified number of OS events in the total population. The final analysis of PFS will be aligned with the first OS interim analysis.

For the Phase II/III study with an enrollment pause, the first interim analyses of OS (IA1, adaptive decision making) will occur when the first 300 participants have a minimum follow-up of 9 months. A futility criterion of p-value > 0.1 for log-rank test of OS is pre-specified for adaptive decision making. If the futility criterion is not met at the first interim analysis (IA1), the study will continue as a Phase III study and enrollment of an additional 340 participants to a total of 640 participants will occur. If the futility criterion is met in the OS analysis, the study will stop for futility. The timing of the second interim

analyses will be triggered by the pre-specified number of OS events in the total population. The final analysis of PFS will be aligned with the second OS interim analysis.

The nominal significance levels for the interim and final analyses of OS will be determined by the Lan-DeMets spending function based upon the O'Brien-Fleming boundary. The futility bounds of this study are non-binding and the bounds are considered guidance rather than strict bounds.

[Table 13](#) and [Table 14](#) summarizes the required number of events, sample size and decision guidance for the planned PFS and OS analyses for the 2 Phase III study scenarios, respectively. Efficacy boundaries and non-binding futility boundaries are based on initially assigned type I error rate before any alpha re-allocation and projected number of events at study mile stones. The actual boundaries will be determined from the actual number of interim analyses conducted and from the actual number of events, at the time of the specified interim analysis using the alpha- and beta- spending functions. Actual futility bounds will be updated if overall beta is changed with respect to alpha reallocation.

Results of the interim analyses will be reviewed by an independent data monitoring committee (IDMC). Further details of interim analyses are provided in the IDMC Charter. Any change to the planned event size will be described in the statistical analysis plan before any unblinding of the data.

Table 13 Summary of Number of Events, Sample Size and Decision Guidance at the Planned Interim and Final Analyses for Phase III Study with No Pause in Enrollment

Analysis	Key Endpts	Expected Number of Events at the Planned Analysis (Information Fraction)	Efficacy Boundary ¹		Non-binding Futility Boundary ¹	
			p-value	Cumulative Alpha	p-value	Cumulative Beta
IA1 : Final PFS Analysis (H3, H4); Interim OS Analysis ¹ (H1, H2)	PFS	~470 (100%)	0.0001	0.0001	NA	NA
	OS	~310 (76%)	0.01	0.01	0.619	0.0007
IA2 : Interim OS Analysis ² (H1, H2)	OS	~375 (92%)	0.016	0.019	0.143	0.017
FA : Final OS Analysis (H1, H2)	OS	~410 (100%)	0.019	0.0249	0.019	0.094

Abbreviations: Endpts=endpoints; FA: final analysis; H=hypothesis; IA: interim analysis; NA: not applicable; PFS=progression-free survival; OS=overall survival

1. Efficacy boundaries and non-binding futility boundaries are based on initially assigned type I error rate before any alpha roll-over and projected number of events at study mile stones. Actual efficacy boundaries will be based on the actual number of interim analyses conducted and actual numbers of events available at study milestones. Actual futility bounds will be updated if overall beta is changed with respect to alpha roll-over.
2. The timing of interim analyses and final analysis for OS may be delayed in the presence of non-proportional hazards.

Table 14 Summary of Number of Events, Sample Size and Decision Guidance at the Planned Interim and Final Analyses for Phase II/III Study with Pause in Enrollment

Analysis	Key Endpts	Expected Number of Events at the Planned Analysis (Information Fraction)	Efficacy Boundary ¹		Non-binding Futility Boundary ¹	
			p-value	Cumulative Alpha	p-value	Cumulative Beta
IA1 : Interim OS Analysis ^{1, 3} (H1, H2)	OS	~136 (32%)	0.00007	0.00007	0.1	0.263
IA2 : Final PFS Analysis (H3, H4); Interim OS Analysis ² (H1, H2)	PFS	~456 (100%)	0.0001	0.0001	NA	NA
	OS	~315 (74%)	0.009	0.009	NA	0.263
FA : Final OS Analysis (H1, H2)	OS	~425 (100%)	0.022	0.0249	0.022	0.288

Abbreviations: Endpts=endpoints; FA: final analysis; H=hypothesis; IA: interim analysis; NA: not applicable; PFS=progression-free survival; OS=overall survival

1. Efficacy boundaries and non-binding futility boundaries are based on initially assigned type I error rate before any alpha roll-over and projected number of events at study mile stones. Actual efficacy boundaries will be based on the actual number of interim analyses conducted and actual numbers of events available at study milestones. Actual futility bounds will be updated if overall beta is changed with respect to alpha roll-over.
2. The timing of interim analyses and final analysis for OS may be delayed in the presence of non-proportional hazards.
3. Represents the OS adaptive decision analysis timepoint. If OS reaches the futility boundary then no further OS analyses will be performed and IA1 becomes the end of Phase II for OS.

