9.2. Sample Size Determination

The adaptive Phase II/III study design allows the study to be a Phase II/III or Phase III study, subject to the outcome of the efficacy analysis at the adaptive decision points

The first adaptive decision point that informs on Study 209227 design results from Study 209229, which are data external from Study 209227. The timing of the analysis for adaptive decision in Study 209229 will occur when approximately 100 PD-L1 CPS \geq 1 participants have a minimum follow-up of 6 months and will be conducted using ORR/DCR per RECIST v1.1 based on investigator assessment. The adaptive decision criteria are defined positive if there is at least an 8% improvement of ORR in the GSK3359609 in combination with pembrolizumab arm compared with the pembrolizumab/placebo arm in the PD-L1 CPS \geq 1 population of Study 209229 [GlaxoSmithKline Document Number [2019N403389_03](#)].

- If the analysis for the adaptive decision in Study 209229 (INDUCE-3; NCT04128696) is positive (Δ ORR \geq 8%), then Study 209227 will become a Phase III study that includes no pause in enrollment.
- If the analysis for the adaptive decision in Study 209229 is to remain as a Phase II study ($0\% \leq \Delta$ ORR < 8% , or Δ ORR < 0% and Δ DCR > 0%), then Study 209227 will be a Phase II/III adaptive study and the sample size will depend upon the outcome of the interim OS analysis within Study 209227; refer to Section 9.2.2 and Section 9.5 for details.
- If the analysis for the adaptive decision in Study 209229 is to stop for futility (Δ ORR < 0% and Δ DCR < 0%) then Study 209227 may stop.

Should a Phase II/III study be decided, then the Study 209227 will randomize approximately 300 participants with a 1:1 ratio between the GSK3359609 in combination with pembrolizumab plus platinum-based chemotherapy arm and the placebo in combination with pembrolizumab plus platinum-based chemotherapy arm. Assuming the aforementioned prevalence rate of PD-L1 CPS status, a sample size of 300 participants will approximately provide 129 PD-L1 CPS \geq 20 participants, 126 PD-L1 1 \leq CPS < 20 participants and 45 PD-L1 CPS < 1 participants.

Should a Phase III study be decided, the study will randomize approximately 640 participants with a 1:1 ratio between the GSK3359609 in combination with pembrolizumab and platinum-based chemotherapy arm and the placebo in combination

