Under the proportional hazard assumption with 425 events at the final analysis, this study has 71.2% power to demonstrate superiority of OS at the one-sided alpha level of 2.49% with a true HR of 0.72. If the futility boundary of p-value > 0.1 is not crossed at IA1, there is 98.8% probability to demonstrate superiority of OS with a true HR of 0.72. Success for OS at the final analysis approximately corresponds to an observed hazard ratio of 0.82.

Scenario 2 – non-proportional hazards with delayed separation of OS curve and heavy tail

A simulation study was performed with same piecewise time varying hazard ratios described in Section 9.2.1. The simulation showed the final analysis will be delayed by approximately 3 months compared with the proportional hazard scenario. Under the non-proportional hazard assumption with 425 events at the final analysis, the study has 47.9% power to demonstrate superiority of OS at the one-sided alpha level of 2.49% with a true HR of 0.72 at the final analysis. If the futility boundary of p-value > 0.1 is not crossed at IA1, there is 98.8% probability to demonstrate superiority of OS with a true HR of 0.72. Success for OS at the final analysis approximately corresponds to an observed hazard ratio of 0.82.

Progression-free Survival

The final PFS analysis will be carried out at the time of the second interim analysis (IA2) for OS; with approximately 456 PFS events across the 2 arms. With 456 PFS events, the study has 92% power to demonstrate superiority in PFS when the true hazard ratio for PFS is 0.62 at type I error rate of 0.01% (one-sided).

The sample size and power calculation of PFS is based on the following assumptions:

1. PFS follows an exponential distribution with a median of 5 months in the placebo in combination with pembrolizumab and platinum-based chemotherapy arm
2. Hazard ratio is 0.62 for PFS between the GSK3359609 in combination with pembrolizumab and 5FU/platinum chemotherapy arm and the placebo in combination with pembrolizumab and 5FU/platinum chemotherapy arm
3. Enrollment consists of 2 phases. The first phase is an enrollment period of ~15 months for 300 participants, followed by a 12 month pause in enrollment. The second phase is an enrollment period of ~18 months for 340 participants
4. Yearly dropout rate of 10%

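### In the Phase II/III design, the 92% PFS power holds only if the study passes the OS futility look and reaches IA2, unlike the OS power beside it, which deducts the stop

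*Protocol*

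**What the plan says.** **The gate.** In the Phase II/III design the study "will randomize approximately 300 participants with a 1:1 ratio" (protocol 9.2). It adds 340 more only if the OS log-rank p-value at IA1 is not above 0.1. On the other branch, "If the futility criterion is met in the OS analysis, the study will stop for futility" (9.5). The same section adds: "The futility bounds of this study are non-binding and the bounds are considered guidance rather than strict bounds".

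**PFS.** Section 9.5 says: "The final analysis of PFS will be aligned with the second OS interim analysis". Section 9.2.2 agrees ("The final PFS analysis will be carried out at the time of the second interim analysis (IA2) for OS"), and Table 14 has no PFS row at IA1. The stated power is: "With 456 PFS events, the study has 92% power to demonstrate superiority in PFS when the true hazard ratio for PFS is 0.62", at one-sided 0.01%.

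**OS, same section.** Under Scenario 1, "this study has 71.2% power to demonstrate superiority of OS at the one-sided alpha level of 2.49% with a true HR of 0.72", with a separate 98.8% if the futility bound is not crossed. Scenario 2 gives 47.9%, again with 98.8%. Table 14 puts cumulative beta at 0.263 at IA1 and 0.288 at the final analysis.

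**After a stop.** Protocol 4.1 ends enrollment and OS analyses and does not mention PFS. Footnote 3 of Table 14 likewise refers only to OS. SAP Appendix 5 says that after a futility stop BICR is dropped but a final PFS analysis on investigator assessment remains. SAP 2.2 keeps the multiplicity scheme if the study stays in Phase II.

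**The concern.** Section 9 counts the study as successful on either OS or PFS in the total population. A reader of 9.2.2 sees a 71% route through OS and a 92% route through PFS, and may take PFS as the safer one. Both are exposed to the same early OS look, taken at 32% of the OS information. For OS the protocol gives the power with the stop deducted and the power given that the stop is passed. For PFS it gives only the second kind, without saying so. The two headline powers therefore treat one rule in two ways, and the PFS route looks stronger than the design makes it.

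**Working it through.** **1. Reproduce the 92%.** Inputs (9.2.2): 456 events, HR 0.62, one-sided alpha 0.0001, 1:1 allocation.
Power = Φ(√(456/4)·ln(1/0.62) − 3.719) = Φ(5.104 − 3.719) = 91.7%. This matches, so 92% is a fixed-event power with no allowance for stopping.

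**2. Reproduce the OS figures.** Inputs (Table 14): 136 OS events at IA1, HR 0.72, stop if one-sided p > 0.1.
- P(pass IA1) = Φ(√(136/4)·ln(1/0.72) − 1.2816) = Φ(1.9155 − 1.2816) = 73.7%, so beta = 0.263, as in Table 14. A two-sided reading would give 60.7%, which does not match.
- Simulating the Table 14 boundaries at 136/315/425 events gives OS power of 71.3% with the stop obeyed (stated: 71.2%) and 91.9% with it ignored.

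The stated OS power therefore assumes that the stop is obeyed.

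**3. PFS success at IA2 with the stop obeyed, Scenario 1.** This needs both a pass at IA1 and significance on 456 events.
- Bounds for any dependence: 0.737 + 0.917 − 1 = 65.4% up to 73.7%.
- The documents give no OS/PFS correlation, so I assume 0 to 0.6 between the two test statistics at IA1. PFS data accruing up to IA2 dilute this by √(231/456) = 0.71 (231 comes from step 4), so 0.6 becomes 0.43.
- Correlation 0: 0.737 × 0.917 = 67.6%. Correlation 0.6 (bivariate normal): 70.1%.

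**4. Credit for a PFS test after a stop.** The documents give no event count. Assumptions: 300 participants accrued uniformly over 15 months, cut-off at month 24, exponential PFS with control median 5 months (λ = ln2/5 = 0.1386; 0.62 × λ in the experimental arm), and 10% yearly dropout (δ = −ln(0.9)/12).
- Expected events per arm = 150 × the average over entry time u in 0-15 of λ/(λ+δ)·[1 − exp(−(λ+δ)(24−u))]. The two arms sum to about 231.
- Power at 0.01% = Φ(√(231/4)·ln(1/0.62) − 3.719) = Φ(3.634 − 3.719) = 46.6%.
- P(stopped at IA1 and PFS significant): 0.263 × 0.466 = 12.3% at correlation 0; 4.3% at 0.6.
- Total: 67.6 + 12.3 = 79.8% (before rounding) down to 70.1 + 4.3 = 74.4%. With 200 to 250 events at the stop (power 37-52%), the total runs from about 73% to 81%.

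**5. Scenario 2.** The pass rate is not stated. It is implied by 47.9/98.8 = 48.5%; simulating the piecewise hazards to 136 events gives 49.0%.
- At IA2: 0.485 + 0.917 − 1 = 40.2% up to 48.5%.
- With a PFS test after a stop: 0.445 + 0.240 = 68.5% at correlation 0; 0.469 + 0.138 = 60.7% at 0.6.

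Two cautions apply:
- The 98.8% is not a safe divisor. In Scenario 1, 71.2/73.7 = 96.6%, not 98.8%.
- IA1 is triggered by nine months of follow-up, not by 136 events. Simulating a 24-month cut-off gives about 147-149 OS events and pass rates of 75.5% (Scenario 1) and 57.8% (Scenario 2). The Scenario 2 bounds at IA2 then become 49.5% to 57.8%.

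**The case against.** The best defence is that 92% is not an error. The sentence opens by fixing 456 events, and at that count the figure is right. A fixed-event power and a group-sequential power are different quantities, and the futility bound is only guidance. The first part stands: this is not a miscalculation. The guidance argument does not reconcile the two figures. If the bound is disregarded, OS power is 91.9% rather than 71.2%; if it is followed, 92% is not the power of the design.

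A reader might go further and infer that PFS is never tested after a futility stop, so that PFS power is capped at 73.7%. The documents do not support that. Protocol 4.1 and footnote 3 of Table 14 close only enrollment and OS, SAP Appendix 5 keeps a final PFS analysis after a stop, and SAP 2.2 keeps the multiplicity scheme in Phase II. None of these gives an event count, alpha or power for that analysis, so whether H3 is formally tested there remains unclear. The 65-74% is therefore success at IA2 only.

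Alpha passed from OS to PFS could raise the power at IA2, but cannot lift that path above the 73.7% pass rate.

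Finally, the trial ended early and SAP 4.7 says no interim analyses will be performed. The practical consequence is small, although 9.2.2 and Table 14 remain in the current protocol.

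**Conclusion.** The point holds as a reporting inconsistency in the planned Phase II/III design. The 92% is the PFS power given 456 events at IA2, while the OS power next to it deducts the futility stop.

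On the reading used for OS:
- **Scenario 1:** about 65-74% for success at IA2 (68-70% for correlations 0 to 0.6), or about 74-80% if PFS is also tested at 0.01% after a stop.
- **Scenario 2:** roughly 40-50% and 61-69%.

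Neither treatment of PFS after a stop reaches 92%. The Scenario 1 bounds at IA2 use only protocol figures. The narrower ranges rest on the assumed correlation, and the totals also on about 231 PFS events at the stop. The Scenario 2 figures are approximate because they depend on the stated 98.8% and on 136 OS events at IA1; a calendar-triggered IA1 would raise them.

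**What to change.** In protocol 9.2.2:
- Label the 92% as conditional on reaching IA2 with 456 PFS events.
- Beside it, give the unconditional PFS power for both scenarios, on the same reading of the futility rule as the OS power.
- State whether H3 is formally tested after a futility stop, and use the matching figure. If it is tested, give the alpha and expected events, and align 9.5, Table 14 and SAP Appendix 5.

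This is a wording change with no effect on sample size. Its only cost is a less favourable stated PFS power.
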